6.3 Blinding

Participants and CRS staff will be unblinded to participant treatment arm assignments. Laboratory Center (LC) staff will be unblinded to whether a sample is from Part A or Part B, but will remain blinded to treatment assignment within Part A or Part B during sample analysis.

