6.4 Statistical analyses

This section describes the final study analyses, unblinded as to treatment arm assignment. All safety data from enrolled participants will be analyzed according to the initial randomization assignment regardless of how many study-product administrations and how much study product they received. In the rare instance that a participant receives the wrong treatment at a specific study-product administration time, the Statistical Analysis Plan (SAP) will address how to analyze the participant's safety data. Analyses of safety data are modified intentto-treat (MITT), in that individuals who are randomized but not enrolled do not contribute data and hence are excluded. Because of the brief length of time between randomization and enrollment-typically no more than 4 working days-very few such individuals are expected. The primary analysis of mAb concentration and antiviral functional activity data are per-protocol (PP), in that only individuals who receive the expected mAb at the expected dose level within the expected visit window contribute data. Secondary analysis will also involve the MITT cohort, and when necessary, account for the actual specimen collection time and the actual time and dose amount of each product administration.

Analyses for primary endpoints will be performed using SAS and R. Additional software may be used to perform noncompartmental PK and population PK analyses (eg, Monolix). All other descriptive and inferential statistical analyses will be performed using SAS, StatXact, or R statistical software.

No formal multiple-comparison adjustments will be employed for multiple primary or secondary endpoints. However, multiplicity adjustments will be made for certain primary or secondary endpoint assays, as discussed below, when the assay endpoint is viewed as a collection of hypotheses (eg, testing multiple pseudoviruses to determine a positive antiviral functional activity response). Unless otherwise noted, all statistical tests will be two-sided and will be considered statistically significant if p < 0.05.

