6.4.8.1 Safety

During the course of the trial, unblinded analyses of safety data will be prepared approximately every 4 months for review by the SMB. Ad hoc safety reports may also be prepared for SMB review at the request of the HVTN 143/HPTN 109 PSRT.

7 Selection and withdrawal of participants

Participants will be adults who do not have HIV (seronegative), are in overall good health, comprehend the purpose of the study, and have provided written informed consent. Volunteers will be recruited and screened; those determined to be eligible, based on the inclusion and exclusion criteria, will be enrolled in the study. Final eligibility determination will depend on information available at the time of enrollment, including results of screening laboratory tests, medical history, physical examinations, and answers to self-administered and/or interview questions.

Occasionally, investigators encounter volunteers who may not be appropriate for enrollment even if they meet all inclusion/exclusion criteria. Unanticipated medical, psychiatric, occupational, or other conditions may make evaluation of safety and/or other endpoints difficult, making some volunteers poor candidates for retention. In these unusual instances, investigators should use good clinical judgment in considering a volunteer's overall fitness, taking care to avoid unconscious bias.

Determination of eligibility, taking into account all inclusion and exclusion criteria, must be made within 56 days prior to enrollment unless otherwise noted in Sections 7.1 and 7.2.

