9.3 Enrollment and study-product administration visits

Once a volunteer has consented to trial participation and is found to meet all eligibility criteria (see Sections 7.1 and 7.2), the CRS requests the randomization assignment via a Web-based randomization system. Enrollment is simultaneous with first study-product administration. In general, the time interval between randomization and enrollment should not exceed 4 working days. However, circumstances may require a participant's enrollment visit to be changed. This may exceed the 4-day randomization time limit with approval from the clinical trial manager/clinical research manager.

At all study-product administration visits, the following procedures are performed before study-product administration:

- Abbreviated physical examination, including weight, vital signs, and a symptom-directed evaluation by history and/or appropriate physical exam based on participant self-reported symptoms or complaints;
- Assessment of baseline solicited AEs;
- Assessment of concomitant medications (as described in Section 9.2);
- Assessment of any new or unresolved unsolicited AEs/intercurrent illnesses; and
- Clinical laboratory tests including:
 - CBC with differential;
 - Chemistry panel (ALT, aspartate aminotransferase [AST], alkaline phosphatase [Alk Phos], and creatinine); and
 - Urine or serum pregnancy test (for participants who are of pregnancy potential). Persons who are NOT of pregnancy potential due to having undergone hysterectomy or bilateral oophorectomy (verified by medical records), are not required to undergo pregnancy testing. For pregnant participants, see Section 9.11.

Following completion of all procedures in the preceding list, and if available results indicate that study-product administration may proceed, study product is administered (see Sections 8.3 and 8.4).

Administration of all infusions during a study-product administration visit must be accomplished within 1 calendar day.

Immediately following study-product administration, the participant remains in the clinic for observation for about 1 hour. See the HVTN 143/HPTN 109 SSP for details regarding study-product administration visit procedures. Before leaving the clinic, the participant is given the Participant Diary and is instructed on how to complete it. The CRS will make arrangements to be in contact with the participant as described in Section 9.8.

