Appendix I Procedures at CRS for Part B

Visit	01 ¹	02 ²	03	04	05	06	07	08	09	10	11	12	Post
Day		D1	D4	D7	D29	D57	D113	D169	D173	D225	D304	D365	
Week		W0	W0	W0	W4	W8	W16	W24	W24	W32	W40	W48	
Procedure	Scr	Inf 1						Inf 2	Phone contact				
Study procedures													
Signed screening consent (if used)	Х	—	—							_			
Assessment of Understanding (AoU)	Х		_		_								_
Signed protocol consent	Х		_		_								_
Medical history	Х		_		_								
Complete physical exam	Х	_				_						Х	
Confirm eligibility, obtain demographics, randomize	Х	_			_	_				_		_	_
Infusion		Х	_					Х		—	—	—	
Solicited AE assessment ³		X ³	X ³	X ³				X ³	X ³				
Abbreviated physical exam		Х	Х	Х	Х	Х	Х	Х		Х	Х	—	—
Risk-reduction counseling ⁴	Х	Х	—	—	Х	Х	Х	Х		Х	Х	Х	—
Contraception status assessment ⁵	Х	Х	—	—	Х	Х	Х	Х		Х	Х	Х	—
Social impact assessment		Х	—	—	Х	Х	Х	Х		Х	Х	Х	—
Behavioral assessment questionnaire ⁶	Х		—							_		Х	—
Social impact assessment questionnaire			—			Х				_		Х	—
Acceptability questionnaire		Х	—		—			Х		_			—
Outside testing and belief questionnaire			_		_							Х	
Concomitant medications	Х	Х	Х	Х	Х	Х	Х	Х		Х	Х	Х	—
Intercurrent illness/unsolicited AE assessment		Х	Х	Х	Х	Х	Х	Х		Х	X	Х	
HIV assessment ⁷	Х						Х			Х		X	
Confirm HIV test results provided to participant		Х										X	Х
Specimen collection ⁸	Х	Х	Х	Х	Х	Х	Х	Х		Х	Х	Х	
Footnotes for Appendix I:

¹ Screening may occur over the course of several contacts/visits, up to and including day 1 prior to study-product administration.

- ² Specimens collected at day 1 may be obtained within the 14 days prior to study-product administration, except for a pregnancy test, which must be performed on urine or blood specimens within 48 hours prior to study-product administration.
- ³ Solicited adverse event (AE) assessments are performed daily for at least 3 full days following study-product administration. CRS staff will review and reconcile the diary with the participant and then report solicited AEs. Participant diary reconciliation may happen as the data is available (see the HVTN 143/HPTN 109 study-specific procedures [SSP]). For Part B participants' second infusion solicited AE data collection: remote documentation of the participant diary may occur after the solicited AE assessment period and the next clinic visit (visit 9) (see the HVTN 143/HPTN 109 SSP).
- ⁴ Includes transmission risk-reduction counseling for participants living with HIV.

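### Part B assignment may precede first infusion by 4 or more working days while some eligibility checks remain open, and nothing withholds the arm from clinic staff or volunteer in that interval

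*Protocol*

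**What the plan says.** Part A is not randomized, so the point concerns Part B (Groups 4 to 8) only.

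- **Order of steps.** Section 9.3 says that a volunteer who has consented and "is found to meet all eligibility criteria (see Sections 7.1 and 7.2), the CRS requests the randomization assignment via a Web-based randomization system". It then says "Enrollment is simultaneous with first study-product administration".
- **Interval.** "In general, the time interval between randomization and enrollment should not exceed 4 working days". If the visit has to move, "This may exceed the 4-day randomization time limit with approval from the clinical trial manager/clinical research manager". No upper limit is given.
- **When eligibility closes.** Section 7 says "Final eligibility determination will depend on information available at the time of enrollment". Inclusion criterion 19 needs a negative pregnancy test within 48 hours before first product. Exclusion criterion 23 applies blood pressure limits at enrollment. Section 9.2 lets screening run up to the infusion on Day 1. Section 9.3 lists a pre-infusion review (vital signs, symptoms, medications, intercurrent illness, laboratory tests), and infusion depends on it.
- **Who knows the arm.** Section 6.2 sends the assignment to the site pharmacist. Section 6.3 says "Participants and CRS staff will be unblinded to participant treatment arm assignments", without saying when they learn it.
- **Analysis.** Section 6.4 states that for safety "individuals who are randomized but not enrolled do not contribute data and hence are excluded", and expects few such cases because the interval is short. The per-protocol set for concentration and functional activity admits only people dosed as planned.

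**The concern.** In an open-label trial, what protects the randomized comparison after assignment is that nobody decides whether to treat while knowing the arm. Here part of that decision can fall after assignment. The arms differ widely: Group 4 receives 5+5+5 = 15 mg/kg in total per visit and Group 8 receives 40+40+40 = 120 mg/kg, a ratio of 120/15 = 8. A site doctor hesitating over a borderline finding, or a volunteer having second thoughts, could reasonably be swayed by that.

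Someone dropped at that stage contributes to no analysis. If dropping depends on the arm, the groups compared by the Kruskal-Wallis tests on solicited AE severity (6.4.3.1), and by the Wilcoxon and Kolmogorov-Smirnov-type tests on magnitude-breadth curves (6.4.5.1), are no longer purely the groups that chance produced. That few cases are expected does not make them independent of arm.

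**Working it through.** **1. The plan's own figure.** The block scheme in Section 6.2 is seven blocks at 1:1:1:1:4 and one at 1:1:1:1:2.
- Groups 4 to 7: 7×1 + 1 = 8 each.
- Group 8: 7×4 + 2 = 30.
- Part B: 4×8 + 30 = 62. With 15 in Part A, the total is 77.

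This agrees with Section 6.1.

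**2. Can every criterion be settled at assignment?** Four working days span at least 4×24 = 96 hours, and more across a weekend. The pregnancy-test window opens 48 hours before infusion, so with a 4-day interval it opens 96 − 48 = 48 hours after assignment. For any interval longer than 48 hours, criterion 19 cannot yet have been met when the assignment is requested. Blood pressure at enrollment is in the same position whenever assignment precedes the infusion visit, because enrollment is the infusion. The statement in Section 9.3 that all criteria are met first therefore cannot be literally true for every permitted interval.

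**3. Is the arm withheld meanwhile?** Section 6.2 names the pharmacist as recipient, Section 6.3 makes site staff and participants unblinded, and Section 9.3 has the site request the assignment. None of them delays disclosure. Section 8.3 requires a prescription before the first preparation but does not say whether the prescriber knows the arm.

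**4. What happens to those dropped?** They never enroll, so the MITT rule removes them. They are not dosed, so the per-protocol rule removes them too.

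**5. How often might this occur?** The protocol gives no rate, so the rates q below are assumptions. Expected number = 62q. Chance of at least one = 1 − (1 − q)^62.

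| Assumed q | Expected of 62 | Chance of at least one |
|---|---|---|
| 1% | 0.6 | 46% |
| 2% | 1.2 | 71% |
| 5% | 3.1 | 96% |
| 10% | 6.2 | over 99% |

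These figures show how likely it is that any case arises. They do not measure bias, which also depends on how far dropping is related to arm and outcome. Nothing in the protocol informs that.

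**The case against.** The other side has a good deal to say, and most of it limits the point.

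- **Section 9.3 puts eligibility before assignment**, so what remains open is mainly a final check, and the named items (blood pressure limits, pregnancy test) are largely objective. This stands as a limit. It does not dispose of the timing conflict in step 2, the wider Day 1 review, or a volunteer's change of mind. The Section 7 remark that investigators may judge a volunteer unsuitable despite meeting the criteria concerns eligibility in general and should not be read as a licence to exclude after randomization.
- **The assignment goes to the pharmacist.** Correct. A reader might infer that clinic staff and volunteers certainly know the arm at the last decision. The protocol does not say so; it only fails to prevent it. The study-specific procedures, which are not at hand, may add a restriction.
- **Appendix I.** Its row "Confirm eligibility, obtain demographics, randomize" sits under visit 1, from which a reader might infer that randomization must happen early. The column's footnote lets screening extend to Day 1 before infusion, so late randomization is already allowed, though not required.
- **Loss from small arms.** A reader might infer that one case cuts an arm from 8 to 7. Enrollment targets count infused people, and no section says such a volunteer would not be replaced. That loss is not shown.
- **The exclusion rule is disclosed and sensible.** Never-infused people have no post-product data, so no dosed participant's data are lost. A by-arm disposition table is commonly left to the SAP, and Section 3.3 already requires screening and enrollment logs with reasons.
- **The primary concentration and neutralization objectives are called descriptive** in Sections 6.1.2 and 6.1.3. This narrows the exposure to the between-arm tests but does not remove it.

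**Conclusion.** The point holds in a limited form. The protocol allows an interval of 4 or more working days, without a cap, between assignment and first infusion. It leaves some criteria to be settled inside that interval, does not withhold the arm from unblinded clinic staff or the volunteer, and drops those not infused from both analysis sets. Selective exclusion after randomization is therefore possible, and Section 9.3 conflicts with the sections that fix eligibility at enrollment.

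It would be tempting to conclude that allocation concealment is broken. The documents do not support that: the sequence is computer generated, released through a web-based system, and requested only after consent and eligibility assessment. The risk begins at assignment.

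The size of any bias cannot be computed. The frequencies shown rest on assumed drop-out rates of 1% to 10%. The consequence is confined mainly to the comparisons in Sections 6.4.3.1 and 6.4.5.1. The change is worth making because it is cheap, not because harm to the results has been demonstrated.

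**What to change.** 1. In Sections 6.2 and 9.3, state that in Part B the assignment is released to the site pharmacist only, and is not disclosed to clinic staff or the volunteer until the Day 1 pre-infusion eligibility checks are recorded as passed. Early release to the pharmacist keeps the lead time for thawing (at least 1 hour for VRC01.23LS) and preparation.
2. Match the prescription step in Section 8.3, so that it can be completed with the participant's weight and without the arm being known to the prescriber.
3. Reconcile the Section 9.3 statement that all criteria are met before assignment with Section 7, criteria 19 and 23, and Section 9.2, which settle some of them at or near enrollment. The criteria themselves need not change for this purpose.
4. Keep the MITT set, and report randomized-not-infused volunteers by arm and reason, here or in the SAP.

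**Cost.** Protocol wording, a pharmacist-only release setting in the existing web system, and one disposition table. Clinic staff would learn the arm only on the day; each product has the same stated infusion time of about 30 to 60 minutes (Sections 8.4.2 to 8.4.4), so visit planning need not depend on arm. Some prepared product may be wasted when a check fails, since a prepared VRC01.23LS container lasts at most 4 hours including infusion. Refusal by a volunteer after disclosure is not prevented, which is why item 4 is still needed.

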9.3.1 Managing Ab reactions

Since VRC01.23LS, PGT121.414.LS and PGDM1400LS are human mAbs, rather than murine or chimeric mAbs, which target a viral antigen, and rather than human-cell surface antigens, serious Ab reactions are expected to be rare. Nevertheless, participants will be closely monitored in the clinic during study-product administration and during a post–study-product-administration observation period.

CRS staff are trained to recognize suspected Ab reactions and provide immediate medical care consistent with the HVTN 143/HPTN 109 SSP. Medications used to treat Ab reactions may include acetaminophen, antihistamines, and/or corticosteroids. CRSs are also equipped with additional emergency medical supplies to provide other immediate medical intervention, if indicated, and are near medical emergency services. Should the need arise, CRSs may transfer the participant, once stabilized, to a tertiary care center for further management.

The following procedures should be performed after an Ab reaction:

- Ab reaction clinical assessment; and
- Ab reaction blood collection.

For detailed management of Ab reactions, see the HVTN 143/HPTN 109 SSP.

9.4 Follow-up visits

The following procedures are performed at **scheduled follow-up visits**, as specified in Appendix H and Appendix I:

- Risk-reduction counseling (as described in Section 9.5);
- For participants of pregnancy potential, contraception status assessment (as described in Sections 9.2 and 9.6). In persons who are confirmed pregnant, contraception status assessment is not required;
- Assessment of new or unresolved social impacts (CRS staff will ask participant about the status of any unresolved social impacts and if they have experienced any new social impacts as a result of the trial participation);
- Assessment of new or continuing concomitant medications (as described in Section 9.2);
- Assessment of new or unresolved AEs/intercurrent illnesses;
- Administration of the social impact assessment questionnaire (types of impacts assessed involve personal relationships, health insurance, life insurance, educational or employment opportunities, housing, immigration, or travel);
- Administration of a questionnaire that asks the participant about any HIV testing they may have received outside of the study;
- HIV assessment, including pretest counseling and HIV testing. A subsequent follow-up contact is conducted to provide post-test counseling and to report results to participant;

- Confirm that participants received HIV test results from previous visit. If not, provide test results and post-test counseling as appropriate;
- Abbreviated physical examination, including weight, vital signs, and a symptom-directed evaluation by history and/or appropriate physical exam based on participant self-reported symptoms or complaints;
- Complete physical examination, including weight and vital signs, and clinical assessments of head, ears, eyes, nose, and throat; neck; lymph nodes; heart; chest; abdomen; extremities; neurological function; and skin;
- Specimen collection (should be completed per Appendix F and Appendix G); and
- Clinical laboratory tests including:
 - CBC with differential;
 - Chemistry panel (ALT, AST, Alk Phos, and creatinine);
 - Urine dipstick (urinalysis if appropriate; see Section 9.7); and
 - Urine or serum pregnancy test (for participants who are of pregnancy potential). Persons who are NOT of pregnancy potential due to having undergone hysterectomy or bilateral oophorectomy (verified by medical records), are not required to undergo pregnancy testing. During follow-up in persons who are confirmed pregnant, contraception status assessment is not required, unless clinically indicated.

9.4.1 Interim contacts

CRSs may report safety information obtained at a contact other than the regularly scheduled visits. These contacts are reported as interim visits.

9.5 HIV counseling and testing

HIV counseling will be performed in compliance with the CDC's guidelines or other local guidelines for HIV counseling and referral. HIV testing will be performed in accordance with the protocol-specific HIV testing algorithm following enrollment.

Participants will be counseled routinely during the trial on the avoidance of HIV acquisition.

Potential participants identified during screening as having acquired HIV are not enrolled. Potential and enrolled participants identified as having HIV will be referred for medical treatment, counseling, and management of their HIV. With respect to enrolled participants who acquire HIV during the study, see Section 9.12.

It is theoretically possible that an anti-HIV mAb may suppress viral replication, which can reduce the ability to detect HIV, even if a person has actually acquired HIV.

An anti-HIV mAb is not likely to directly affect the assays used to detect HIV-1 acquisition.

9.6 Monoclonal Ab-associated reactivity

Tests of human plasma containing anti-HIV mAbs have been conducted using a variety of commercially available HIV test kits. At high plasma concentrations, reactive or indeterminate results have been observed on some test kits. See the HVTN 143/HPTN 109 SSP for further detail. Thus, there is a possibility that receipt of the study product will cause a reactive result on some currently available HIV test kits, especially if testing occurs close to study-product administration timepoints.

Study staff will advise study participants to confine their HIV testing while in the study to that provided through the CRS. Staff will also inform study participants of the likelihood of routine HIV testing being offered or performed outside the study CRS at emergency rooms, clinics, and medical offices, and will inform participants of their right to opt out of HIV testing outside the study site. CRS staff should inform study participants if local and/or state/regional policies and regulations permit medical providers to perform HIV testing without first informing patients. If this is the case, then CRS staff should advise study participants if positive results must be reported to local public health authorities. CRS staff should provide participants with CRS contact information and should encourage participants to ask medical providers to contact the CRS. The CRS can verify that the participant is in an HIV mAb clinical trial and should only be tested at the study CRS.

